6.3.4. Randomized Treatment Temporary Interruption

Every effort must be made to continue randomized treatment and to complete study visits, where able; however, sites should contact PPD Remote Site Monitor-Local if a subject cannot return to the research site on a temporary basis for any one of the following situations:

- Subjects who are hospitalized for any duration.
- HD or PD subjects receiving oral daprodustat or PD subjects receiving SC darbepoetin alfa who cannot return to the site for a period >5 weeks
- HD subjects receiving IV rhEPO who cannot return to the site in time for the next dosing interval.

In exceptional circumstances, local standard of care for anemia management during this time period may be considered based on consultation with the PPD Medical Monitor. If non-study ESAs are administered, doses should be recorded on the Prior/Concomitant Medications – ESA eCRF page.

6.3.5. Randomized Treatment Discontinuation

The sponsor will inform investigators when they should have subjects come in for an End of Study visit based on the projected occurrence of 664 first MACE. Subjects will stop taking randomized treatment the day of the End of Study visit.

For those subjects who permanently discontinue randomized treatment, see Section [5.5.1](#) for study visit details.

Anemia therapy may recommence, as required, once randomized treatment has been discontinued.

6.4. Blinding

This is an open-label study; however, the sponsor is blinded to treatment assignment for both the main study and ABPM sub-study. Randomized treatment will have the dose strength on the label. A detailed Blinding Plan will describe the procedures that will be implemented in order to minimize the extent to which this blind may be compromised.

6.5. Packaging and Labeling

Daprodustat tablets are packed in white, opaque high density polyethylene (HDPE) bottles with child-resistant closures. The contents of the label will be in accordance with all applicable regulatory requirements.

6.6. Preparation/Handling/Storage/Accountability

No special preparation of placebo run-in or randomized treatment is required.

Only subjects enrolled in the study may receive placebo run-in and subsequently, randomized treatment and only authorized site staff may supply placebo run-in and randomized treatment. All placebo run-in and randomized treatment must be stored in a secure environmentally controlled and monitored (manual or automated) area in accordance with the labeled storage conditions with access limited to the investigator and authorized site staff.

The investigator, institution, or the head of the medical institution (where applicable) is responsible for placebo run-in and randomized treatment accountability, reconciliation, and record maintenance (i.e. receipt, reconciliation and final disposition records).

Further guidance and information for final disposition of unused placebo run-in and randomized treatment is provided in the SRM.

Under normal conditions of handling and administration, placebo run-in and randomized treatment are not expected to pose significant safety risks to site staff.

A Material Safety Data Sheet (MSDS)/equivalent document describing occupational hazards and recommended handling precautions either will be provided to the investigator, where this is required by local laws, or is available upon request from GSK.

6.7. Compliance with Randomized Treatment Administration

Randomized subjects, who administer randomized treatment (daprodustat or rhEPO [darbepoetin alfa or epoetin alfa]) at home, will be instructed to return all unused randomized treatment at each clinic visit. A record of the number of daprodustat tablets or rhEPO doses dispensed to and taken by each subject will be maintained and reconciled with randomized treatment and compliance records. Randomized treatment start and stop dates and dosing details, including dates for randomized treatment interruptions and/or dose increases or reductions, will be recorded in the eCRF. At Week 2 and for unscheduled visits, compliance checking will not be performed if the dose of randomized treatment is not changed.

For subjects randomized to rhEPO (darbepoetin alfa or epoetin alfa) who have randomized treatment administered in the clinic, the details of each administered rhEPO dose will be maintained and reconciled with randomized treatment and compliance records. Randomized treatment start and stop dates and dosing details, including dates for randomized treatment interruptions and/or dose increases/reductions, will be recorded in the eCRF.

6.8. Treatment of Randomized Treatment Overdose

There is no specific antidote for overdose with daprodustat. The expected manifestations of daprodustat overdosage include signs and symptoms associated with an excessive and/or rapid increase in Hgb concentration. Daprodustat is highly protein bound; thus, clearance of daprodustat by HD or PD is very low and these are not effective methods to enhance the elimination of daprodustat. Daprodustat metabolites are, in part, cleared via hemodialysis. In the event of a suspected overdose, it is recommended that the appropriate supportive clinical care be instituted, as dictated by the subject's clinical status. Additionally, subjects should be monitored closely for CV events, increased HR and hematologic abnormalities.

Consult the approved product label for information on overdose for darbepoetin alfa and epoetin alfa.

6.9. Treatment after the End of the Study

Subjects will not receive any additional treatment from GSK after completion of the study. The investigator is responsible for ensuring that consideration has been given to post-study care of the subject's medical condition.

6.10. Concomitant Medications and Non-Drug Therapies

Concomitant medications, including over-the-counter medications and supplements, taken during the study will be recorded in the eCRF. Start/stop dates and route of administration will be recorded for general concomitant medications. Additional details (e.g., changes in dose, reason for change, reason for addition or termination) will be recorded for certain medications at each visit (e.g., iron and anti-hypertensive medications).

6.10.1. Permitted Medications and Non-Drug Therapies

Unless specified as a prohibited medication in Section 6.10.2, all concomitant medications should be considered permitted provided they are not contraindicated for the individual subject concerned.

Co-administration of daprodustat with moderate CYP2C8 inhibitors (e.g., clopidogrel, teriflunomide, deferasirox) should be performed with caution. If one of these medications is started, stopped or the dose is changed, Hgb should subsequently be monitored every 4 weeks for the following 12 weeks.

6.10.2. Prohibited Medications and Non-Drug Therapies

Use of any of the following prescription drugs from screening (Week -8) until 7 days after the last dose of randomized treatment is prohibited and will constitute a protocol violation.

- Strong inhibitors of CYP2C8 (e.g., gemfibrozil)
- Strong inducers of CYP2C8 (e.g., rifampin/rifampicin)

No other investigational agents or devices are permitted from study entry through completion of the study, with the exception of the randomized treatment administered for this study.

6.11. Standard of Care

During the study (from screening), investigators are expected to monitor the subject's overall clinical status to ensure standards of care are met to enable consistency of practice with Kidney Disease Improving Global Outcomes (KDIGO) guidelines or local equivalent (e.g., phosphate and albumin).

For this study, specific iron management criteria and a dose adjustment algorithm for randomized treatment will apply. These were developed to reflect global clinical practice.

6.11.1. Iron Management Criteria

Subjects must remain iron replete throughout the study. The investigator will follow the iron management criteria from randomization (Day 1) through the end of the study treatment period for subjects receiving randomized treatment.

Iron therapy will be administered if ferritin is ≤ 100 ng/mL and/or TSAT is $\leq 20\%$. The investigator should choose the route of administration and dose of iron based on the subject's iron status and local clinical practice.

All iron (excluding multivitamins) must be stopped and cannot be administered if;

- Ferritin > 800 ng/mL and TSAT $> 20\%$, or
- TSAT $> 40\%$

Investigators should be guided by local/regional guidelines and may stop administration of iron at a lower ferritin or TSAT level as long as subjects are maintained at a ferritin > 100 ng/mL and TSAT $> 20\%$.

The Steering Committee (Section 10.8.4) will monitor blinded subject iron data in an ongoing fashion to ensure compliance.

6.12. Rescue Therapy

A rescue algorithm is provided to minimize subjects having an inadequate response to the treatment for their anemia for an extended period of time and to enable consistency in the application of rescue therapy across the study. Details are provided in [Table 6](#).

This rescue algorithm **does not** apply to subjects with a low Hgb as a result of an acute or subacute event with an identifiable cause (e.g., GI bleed, blood loss due to surgery or vascular access). In these cases, treatment should be directed to the specific cause and randomized treatment will be continued. If a subject is transfused as part of the treatment, then the randomized treatment will be maintained at the current dose (unless Hgb is ≥ 12 g/dL which requires a dose hold).

Table 6 Rescue Algorithm for Anemia Management

Evaluate Subject for Rescue if: HemoCue Hgb remains <9 g/dL (at a scheduled study visit, Week 4 onwards) despite three ¹ consecutive dose increases above the starting ² or post-rescue ³ dose (where HemoCue Hgb is <9 g/dL prior to each dose increase) OR HemoCue Hgb is <7.5 g/dL despite a dose increase at the prior study visit.	
Step 1: Initial Intervention	While continuing randomized treatment (increase dose if HemoCue Hgb <7.5 g/dL; otherwise maintain current dose), intervene with one or more of the following as dictated by clinical comorbidities 
 - Single course of IV iron up to 1000 mg (in addition to the iron management criteria) - Transfusion of up to two units of packed red blood cells (PRBC) if clinically indicated - Allow additional 4 weeks on randomized treatment (NOTE: this is a required choice; can be combined with either or both of the above).
Step 2: Rescue	Check HemoCue Hgb 4 weeks ±1 week from last study visit; earlier checks of Hgb may be obtained to advise further intervention as clinically indicated. Randomized treatment should be permanently discontinued and the subject should be rescued according to local clinical practice if either, 
 - If HemoCue Hgb remains <9 g/dL despite initial intervention based on the average of two HemoCue Hgb values⁴ 
OR
 
 - More than two units of PRBC were needed for transfusion (and was not related to acute bleeding).

1. Two consecutive dose increases if starting/post-rescue dose is daprodustat 12 mg, epoetin alfa 42000 U per week, or darbepoetin alfa 200 µg over 4 weeks; one dose increase if starting/post-rescue dose is daprodustat 16 mg, epoetin alfa 48000 U per week, or darbepoetin alfa 300 µg over 4 weeks; and no prior dose increase if starting/post-rescue dose is daprodustat 24 mg, epoetin alfa 60000 U per week, or darbepoetin alfa 400 µg over 4 weeks (top dose).
2. For subjects who have switched from HD to PD who are randomized to rhEPO, the baseline dose for the purposes of the rescue algorithm is the new darbepoetin alfa dose.
3. For subjects who previously were evaluated for rescue and who are able to continue in the trial, "post-rescue" dose is the dose of randomized treatment that a subject is receiving at the study visit after initial intervention.
4. Repeat HemoCue Hgb at the same study visit to confirm Hgb (using the same sample); take average of 2 values.

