6.3. Randomized Treatment Starting Dose and Dose Adjustment

6.3.1. Daprodustat Dosing Information

Daprodustat Starting Dose:

The starting dose of daprodustat will be assigned based on prior ESA dose at randomization (Day 1) ([Table 3](#)).

Table 3 Daprodustat Starting Dose

[figure not shown]
ESA Dose at Randomization(Day 1)			Daprodustat Starting Dose
epoetins (incl biosimilars) (U/week IV) ¹	darbepoetin (µg/4week SC/IV) ²	methoxy PEG-epoetin beta (µg/month SC/IV) ^{3,4}	(mg, once daily)
1500 to 2000	20 to 30	30 to 40	4
>2000 to <10000	>30-150	>40 to 180	6
≥10000 to <20000	>150-300	>180 to 360	8
≥20000	>300	>360	12

PEG=polyethylene glycol

1. Standardized rhEPO IV dose (U/week) = 161/113 * (epoetin SC dose (units)) / (frequency) [[Beserab, 2002](#)]
2. Conversion of 250 U:1 µg (epoetin IV:darbepoetin alfa) utilized and rounded to the nearest available dose strength [[Sternier, 2008](#)]
3. Conversion of 1:1.2 µg (darbepoetin alfa:methoxy PEG-epoetin beta)) utilized and rounded to the nearest available dose strength [[Choi, 2013](#)]
4. Conversion of 208 U:1 µg (epoetin IV: methoxy PEG-epoetin beta)

Daprodustat Dose Steps:

The available dose steps of daprodustat are outlined below. Dose adjustments will result in the daprodustat dose being increased or decreased by one dose step at a time. Those receiving the highest dose of daprodustat who require a dose increase will maintain the same dose, while those receiving the lowest dose of daprodustat that require a dose decrease will have doses withheld.

6.3.2. rhEPO Dosing Information

rhEPO Starting Dose:

The starting dose for subjects receiving rhEPO is as follows:

- For subjects with a baseline (Day 1) Hgb ≤11 g/dL

- For subjects already on epoetin alfa (HD subjects) or darbepoetin alfa (PD subjects), the starting dose will be the same as their currently scheduled dose, rounded to the nearest study dose.
- For subjects receiving other types of ESAs, the starting dose will be an IV epoetin alfa (HD subjects) or SC darbepoetin alfa (PD subjects) equivalent dose, rounded to the nearest study dose.
- For subjects with a baseline (Day 1) Hgb >11 g/dL and ≤11.5 g/dL
 - The starting dose of IV epoetin alfa (HD subjects) or SC darbepoetin alfa (PD subjects) will be reduced to the next lowest starting dose with the aim of maintaining Hgb within the range of 10-11 g/dL.

rhEPO Dose Steps:

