Dose-steps of rhEPO are pre-defined in this study (Table 4 and Table 5). The IV epoetin alfa dose steps consist of stepwise increase or decrease in weekly dose of 20 to 33% for most steps, except when weekly doses of 3000 U or when weekly doses are >21000 U per week when further increases are within the 10 to 15% range. The darbepoetin alfa dose adjustment increases and decreases will be in similar steps as compared to epoetin alfa, generally within the 20 to 33% range with a few increases of 50% based on available dose strengths. In some cases, a partial amount of a darbepoetin alfa pre-filled syringe (PFS) will be used to deliver the total 4-weekly dose.

Additional information about the delivery of the respective rhEPO doses is provided in the SRM. Those receiving the highest dose of rhEPO who require a dose increase will maintain the same dose, while those receiving the lowest dose of rhEPO that require a dose decrease will have doses withheld.

For subjects who are on HD two times a week and are randomized to the epoetin alfa arm and require three times a week epoetin alfa dosing, the weekly dose should be split as close to equally, using the study-allocated dose vials of epoetin alfa, across the two dialysis treatments.

Table 4 Epoetin Alfa Dose Steps

Total Weekly Dose	Dose and Frequency
1500	1500 U once a week
2000	2000 U once a week
3000	3000 U once a week
4000	4000 U once a week
5000	5000 U once a week
6000	6000 U once a week
8000	8000 U once a week
10000	10000 U once a week
12000	4000 U three times a week
15000	5000 U three times a week
18000	6000 U three times a week
21000	7000 U three times a week
24000	8000 U three times a week
27000	9000 U three times a week
30000	10000 U three times a week
36000	12000 U three times a week
42000	14000 U three times a week
48000	16000 U three times a week
60000	20000 U three times a week

Table 5 Darbepoetin Alfa Dose Steps

Total 4-Weekly Dose	PFS Dose and Frequency
20 µg	20 µg every 4 weeks
30 µg	30 µg every 4 weeks
40 µg	40 µg every 4 weeks
60 µg	60 µg every 4 weeks
80 µg	80 µg every 4 weeks
100 µg	100 µg every 4 weeks
150 µg	150 µg every 4 weeks
200 µg	100 µg every 2 weeks
300 µg	150 µg every 2 weeks
400 µg	100 µg once a week

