12.6. Appendix 6: Randomized Treatment Dose Adjustment Schemes

HemoCue Hgb (g/dL) at current study visit ¹	HemoCue Hgb change since last study visit ¹	Randomized Treatment Dose Adjustment ⁵
<7.5 ²	Any change	Repeat Hgb and average values ⁶ ; if confirmed, increase to the next higher dose step
7.5 to <9.5	Decreasing or No change ⁷	Increase to the next higher dose step
7.5 to <9.5	Increasing ⁸	Maintain dose
≥9.5 to <10 at two consecutive visits	Decreasing or No change	Increase to the next higher dose step
≥9.5 to ≤11.5	Any change	Maintain dose
>11 to ≤11.5 at two consecutive visits	Increasing or No change	Decrease to the next lower dose step
>11.5 to <12	Decreasing	Maintain dose
>11.5 to <12	Increasing or No change	Decrease to the next lower dose step
≥12 ³	Any change	Repeat Hgb and average values ⁶ ; if confirmed, temporary hold the dose and re-check Hgb at next study visit ¹ ; restart at one dose step lower when Hgb <11.5 g/dL and provided it has been at least 2 weeks from the prior study visit.
Any	>2 g/dL increase over 4 weeks (>1 g/dL increase over 2 weeks ⁴)	Repeat Hgb and average values ⁶ ; if confirmed, decrease to the next lower dose step
Any	>2 g/dL decrease over 4 weeks (>1 g/dL decrease over 2 weeks ⁴)	Repeat Hgb and average values ⁶ ; if confirmed, increase to the next higher dose step

1. "Study visit" refers to mandated study visits (every 4 weeks through Week 52; then every 12 weeks). From Week 52 onwards, additional study visits to check Hgb and dispense randomized treatment (where directed by the IRT system) are required under the following circumstances (additional visits have a visit window of ±1 week):

- When Hgb at last study visit is outside of the target range, i.e., <10 or >11 g/dL: Visit 4 weeks later to assess for dose adjustment.
- When the dose of randomized treatment is changed or restarted in the previous 12 weeks ±1 week: Visits every 4 weeks for 12 weeks.
- When a medication that is a moderate CYP2C8 inhibitor (i.e., clopidogrel, teriflunomide, deferasirox) is started, stopped, or the dose is changed: Visits every 4 weeks for 12 weeks.
- When the investigator determines it clinically necessary to evaluate a subject sooner than 12 weeks later: Visit 4 weeks later to assess for dose adjustment.
- For subjects changing dialysis modality from HD to PD: Visits every 4 weeks for 12 weeks.

2. This rule applies to any mandated visit or unscheduled visit, provided it has been at least 2 weeks from the prior study visit.

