3. This rule applies to any mandated or unscheduled visit.

4. This rule applies to Week 2 and Week 4 visits only.

5. Those receiving the highest dose of randomized treatment who require a dose increase will maintain the same dose, while those receiving the lowest dose of randomized treatment that require a dose decrease will have doses withheld.

6. Repeat HemoCue Hgb at the same study visit to confirm Hgb (using the same sample) and take average.

7. No change may be redefined as an increase of <0.5 g/dL based on the review of blinded instream aggregate Hgb data.

8. Increasing may be redefined as an increase of ≥0.5 g/dL based on the review of blinded instream aggregate Hgb data.

12.7. Appendix 7: Definition of and Procedures for Recording, Evaluating, Follow-Up and Reporting of Adverse Events

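### A subject titrated up to the top dose can stay below Hgb 9 g/dL, or even below 7.5, without ever meeting a rescue criterion

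*Protocol*

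**What the plan says.** Section 6.12 states that the rescue algorithm exists "to minimize subjects having an inadequate response to the treatment for their anemia for an extended period of time" and to make rescue consistent across the study. Table 6 gives two routes into rescue evaluation:

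- **Route 1:** Hgb stays below 9 g/dL after three consecutive increases above the starting or post-rescue dose, each made at Hgb below 9.
- **Route 2:** Hgb is below 7.5 and the dose was increased at the previous visit.

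The counting condition and the second route read "where HemoCue Hgb is <9 g/dL prior to each dose increase) OR HemoCue Hgb is <7.5 g/dL despite a dose increase" at the prior visit. Footnote 1 lowers the required count near the top of each dose ladder and requires "no prior dose increase if starting/post-rescue dose is daprodustat 24 mg, epoetin alfa 60000 U per week" or darbepoetin 400 µg over 4 weeks. Under footnote 3, a post-rescue dose exists only for someone already evaluated once.

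Appendix 6 orders increases over a wider Hgb range: at 7.5 to <9.5 if Hgb is not rising, and at "≥9.5 to <10 at two consecutive visits" if not rising. Its footnote 5 adds "Those receiving the highest dose of randomized treatment who require a dose increase will maintain the same dose"; Sections 6.3.1 and 6.3.2 say the same for each arm. Meeting the rescue criterion is a mandatory reason to stop randomized treatment (Section 5.5), and time to that event is a secondary endpoint (Appendix 2).

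**The concern.** The titration rule and the rescue rule use different Hgb thresholds. Steps taken at Hgb 9.0 to <10 shorten the remaining ladder but add nothing to the count. Once the top dose is reached with the count short, an ordered increase becomes no change, so the count is frozen. Route 2 then has no preceding increase to refer to. Footnote 1 shows that the end of the ladder was considered, but only for subjects who start there or return there after an evaluation.

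The people affected are on the maximum dose with an inadequate response, which is the situation Section 6.12 sets out to limit. Two subjects with the same starting dose, current dose and Hgb can be handled differently. The inferential consequence is confined to time to rescue, which Section 9.4.2.1 treats as exploratory. Low Hgb on treatment belongs to the co-primary estimand by design (Section 9.1.2) and is not bias.

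**Working it through.** **Required count.** Footnote 1 equals min(3, steps left above the starting dose). From Tables 4 and 5, epoetin 36000, 42000, 48000 and 60000 U/week have 3, 2, 1 and 0 steps left; darbepoetin 150, 200, 300 and 400 µg likewise. That gives 3, 2, 1 and 0 required increases, as the footnote states. For daprodustat, 12 to 16 to 24 mg follows from footnote 1. Lower down, the dose-step figure is not shown and 10 mg may or may not be a step, so steps left are 2 from 12 mg, 3 or 4 from 8 mg, 4 or 5 from 6 mg, and 5 or 6 from 4 mg.

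**The two rules side by side.**

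| HemoCue Hgb | Appendix 6 | Counts for route 1 |
|---|---|---|
| <9, not rising (or confirmed <7.5) | increase | yes |
| 9.0 to <9.5, not rising | increase | no |
| 9.5 to <10, second visit running, not rising | increase | no |
| any of these on the top dose | dose maintained | no increase to count |

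**Like-for-like example.** Both subjects start daprodustat 12 mg, so two counted increases are needed.

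| Week | A: Hgb | A: dose, count | B: Hgb | B: dose, count |
|---|---|---|---|---|
| 4 | 8.9 | 16 mg, 1 | 9.4 (falling) | 16 mg, 0 |
| 8 | 8.8 | 24 mg, 2 | 8.9 | 24 mg, 1 |
| 12 | 8.5 | evaluated | 8.5 | 24 mg, 1 |
| 16 to 36 | | | 8.5, 8.4, 8.0, 7.4, 7.3, 7.2 | 24 mg, 1 |

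B's last increase was at Week 8, so route 2 could fire only at Week 12, when Hgb was 8.5. The values of 7.4 and below from Week 28 trigger nothing.

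**Illustrative grid.** Assumed path: Hgb at visit t = max(8.5, start − fall × t), for 13 four-weekly visits to Week 52 (Week 2 omitted). Starts run from 8.6 to 11.5 (30 values) and falls from 0.2 to 1.0 g/dL per visit (9 values): 30 × 9 = 270 paths. On the generous reading used, any run of consecutive increases at Hgb below 9 counts, and an increase at 9 or above resets it. Missed means at least two visits below 9 on the top dose with neither route met.

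| Steps left | 1 | 2 | 3 | 4 | 5 | 6 | 7 |
|---|---|---|---|---|---|---|---|
| Missed of 270 | 152 | 152 | 152 | 50 | 22 | 12 | 0 |

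No path starting at 9.1 or below is missed. A plateau of 8.0, or of 8.8 with starts 8.9 to 11.5 (243 paths), gives the same counts.

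For a start of 10.4:

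| Steps left | Falls missed | Visits <9 on top dose |
|---|---|---|
| 2 (12 mg; 42000 U; 200 µg) | 0.2 to 0.7, and 1.0 | 6 to 11 |
| 3 (36000 U; 150 µg) | same | 6 to 10 |
| 4 (30000 U; 100 µg) | 0.2 to 0.3 | 6 to 7 |
| 5 | 0.2 | 5 |
| 6 | 0.2 | 4 |

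One row by hand, two steps left and fall 1.0: 9.4 at Week 4 (step 1, not counted), 8.5 at Week 8 (step 2, count 1 of 2), then 8.5 at each of the 11 visits from Week 12 to Week 52. With falls of 0.8 or 0.9, both increases happen below 9 and route 1 fires at Week 16. The 0.7 case turns on a single value of exactly 9.0.

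If Hgb falls in a straight line with no plateau, the missed falls are 0.2 to 0.7 with two steps left, 0.2 to 0.5 with three and 0.2 to 0.3 with four. Faster falls are caught, mostly by route 2.

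**The case against.** The logic and the arithmetic are not in dispute; the weight is.

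- **High-dose starters.** The figure of 152 needs three or fewer steps left. Daprodustat 12 mg is assigned only at prior epoetin of 20000 U/week or more (Table 3). On the epoetin ladder the grid shows misses only from 24000 U/week upward, while the protocol's own prior-dose subgroup cut is 7,000 U/week (Section 9.4.4). This stands. The gap is narrow for most epoetin starts, less so on the shorter daprodustat ladder.
- **Constructed paths.** A fixed fall onto a plateau of 8.5 keeps route 2 from firing. This also stands: the grid shows that the gap is reachable and where, not how often.
- **Intended exclusion.** Ignoring increases made at Hgb 9 or above looks deliberate, so evaluating A before B at Week 12 is defensible. B's later persistence on the top dose is not explained by that intent.
- **Safeguards.** The investigator may stop treatment (Section 5.5), standard of care and iron criteria apply (Sections 6.11 and 6.11.1), transfusion is not prohibited, and after Week 52 a 4-week recheck applies "When Hgb at last study visit is outside of the target range". These limit harm. None is a rescue criterion, and discretion does not deliver the consistency that Section 6.12 seeks.
- **Visibility.** Appendix 2 plans summaries of Hgb below 7.5, time below range and dose by visit. As listed, they are not tied to rescue evaluation on the top dose. The analysis plan could cross-tabulate them, so lack of such a table is no fault of the protocol.
- **Timing.** Enrolment is complete (Section 9.2.3), so a rule change would reach only subjects still on treatment.

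**Conclusion.** The concern holds. Read literally, Table 6 with footnotes 1 and 3 and Appendix 6 with footnote 5 leave a state in which a subject on the maximum dose stays below 9, or below 7.5, and no rescue criterion can be met. It can arise in both arms. One uncounted increase is enough from daprodustat 12 mg, epoetin 36000 or 42000 U/week, or darbepoetin 150 or 200 µg. Subjects who take enough consecutive increases below 9 are still caught.

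The grid sizes rest on assumed paths for subjects who do not respond to escalation. The number of subjects affected, and the balance between arms, cannot be derived from the protocol. The change is worth making for patient safety and consistent rescue; the co-primary conclusions do not depend on it.

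**What to change.** Add to Table 6 footnote 1: HemoCue Hgb below 9 g/dL at two consecutive scheduled visits on the top dose (24 mg, 60000 U/week, 400 µg/4 weeks) triggers rescue evaluation with no further increase required. After Week 52, count the additional 4-week visits of Appendix 6 footnote 1. Keep the present waivers, add the matching IRT rule and record the date of the change.

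In the grid this catches every missed path. Where an existing route already fires, the new trigger comes at least 4 weeks later, so it pre-empts neither. At a start of 10.4 with two steps left, it fires at Weeks 16 to 36. It leads to evaluation; Step 1 still allows iron, transfusion and 4 more weeks.

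Alongside, report by arm the number and duration of top-dose visits with Hgb below 9 and no rescue evaluation, and a descriptive time to first meeting the revised criterion. Both use stored dose and HemoCue data.

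The cost is one footnote, one IRT rule and one or two tables. The time-to-rescue criterion changes mid-trial, for subjects still on treatment only. Some more subjects may have to stop randomized treatment, in year 1 no earlier than about 8 + 4 = 12 weeks after reaching the top dose (8 to evaluation, 4 to Step 2). Rescue by local practice can dilute arm differences in an ITT non-inferiority comparison. If that is not acceptable, the by-arm table alone would show how many subjects were affected.
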